2.6. Observation Periods

In this study, four observation periods will be defined. These are Up-to-Day 180, On-Treatment, Post-Randomization and Post-First Dose observation periods. An observation period refers to a time window. Analyses of primary and secondary efficacy as well as safety endpoints will include data within a specified observation period. The primary efficacy endpoint analysis will be performed for more than one observation period as shown in the table below.

Up-to-Day 180 observation period: Primary efficacy composite endpoint analyses (including supportive and sensitivity analyses described in Sections 5.2.3 and 5.2.5 respectively) and secondary efficacy endpoints analyses.

On-Treatment observation period: Primary efficacy composite endpoint supportive analysis. Primary and secondary safety analyses.

Post-Randomization and Post-First Dose observation periods: Primary efficacy composite endpoint supportive analyses.

Analysis of Efficacy Endpoints (Refer to Sections 5.2, 0 for details)			
Analysis Population: ITT			
Endpoint	Observation Period(s)	Endpoint	Observation Period
Primary Efficacy Composite Endpoint Time to the first occurrence of objectively confirmed symptomatic lower extremity proximal DVT, asymptomatic lower extremity proximal DVT, symptomatic lower extremity distal DVT, symptomatic upper extremity DVT, symptomatic non-fatal PE, incidental PE, or VTE-related death	Primary Up-to-Day 180 Sensitivity Up-to-Day 180 Supportive On-Treatment Post-Randomization Post-First Dose	Key Secondary Endpoints 1. Time to first occurrence of objectively confirmed symptomatic VTE events (symptomatic lower extremity proximal DVT, symptomatic lower extremity distal DVT, symptomatic upper extremity DVT, or symptomatic non-fatal PE) or VTE-related deaths Additional Secondary Endpoints 2. Time to all-cause mortality	Key Secondary & Additional Secondary Up-to-Day 180
Safety Endpoints (Refer to Section 6.0 for details)			
Analysis Population: Safety			
Primary Endpoint Time to the first occurrence of objectively confirmed ISTH major bleeding event	Primary On-Treatment	Secondary Safety Endpoints On-Treatment	Secondary On-Treatment
		Time to first occurrence of: 1. Clinically relevant non-major bleeding 2. Minor bleeding 3. Composite bleeding (major, clinically non-major and minor)	

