1.2. Study Design

[figure not shown]
This is a multicenter, randomized, double-blind, placebo-controlled, parallel-group, superiority study comparing the efficacy and safety of rivaroxaban with placebo for primary prophylaxis of VTE (defined as DVT and/or PE) in ambulatory adult men and women, 18 years of age and older, with various cancer types who are scheduled to initiate systemic cancer therapy as a component of their standard of care anticancer regimen, who have a baseline Khorana thromboembolic risk score of ≥ 2 , and are judged by the investigator or qualified designee to be an appropriate candidate for treatment with either placebo (10 mg orally once daily for 180 days) or rivaroxaban (10 mg orally once daily for 180 days) for thrombo-prophylaxis based on their clinical status.

The study consists of 3 periods: a 2-week screening period, a 180-day double-blind treatment period with an End-of-Treatment (EOT) visit [for subjects who permanently stop study drug], and a 30-day post-treatment follow-up period with a Day 210/End-of-Study (EOS) visit. The duration of participation in the study for each subject is approximately 32 weeks.

A target of approximately 700 subjects will be randomly assigned into the study in a 1:1 ratio to 1 of 2 treatment groups (rivaroxaban 10 mg qd and placebo) with approximately 350 subjects per treatment group. Towards the end of the enrollment phase, the planned total of subjects to be randomized into the study was revised to approximately 800 subjects due to a higher than originally anticipated subject discontinuation rate. In addition, subjects will be stratified at randomization by tumor type (APC or non-APC) such that approximately 25% of the subjects randomly assigned are those with APC.

Randomized subjects will continue with their recommended systemic cancer therapy (SCT) during the study period and will be examined by compression ultrasonography (CU) at every 8-week intervals. Subjects permanently discontinuing the study drug will be required to have a CU performed within 2 days of receiving their last dose of study drug.

Figure 1: Schematic Overview of the Study

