1.2.1. Study Drug Discontinuation and Early Withdrawal from Double-Blind Period

As per the protocol (Section 10.2.2), if a subject permanently discontinued study drug before the Day 180 visit/End of double-blind (EODB) period, this would not result in automatic permanent withdrawal of the subject from the study. Subjects are encouraged to make every effort to continue participation in the study and complete the schedule subsequent study visits until the planned end of their study double-blind duration (Day 180/EODB). All outcomes/events data (VTE, vital status (alive/dead), MI, stroke, and other thrombosis events) and safety data (including bleeding events) are collected. If a subject permanently discontinued study drug prior to Day 180 but continued in the study and completed all study visits up to Day 180, then this subject is considered as having ‘completed the double-blind period’ (that is, participated in the study up to the Day 180 visit).

All subjects including those who discontinued prior to Day 180 visit are contacted by telephone for a Day 210/EOS follow-up assessment. Any outcome/event data (including vital status) reported during this telephone visit is collected at this Day 210/EOS visit as agreed upon by the subject informed consent. In the event a subject withdrew consent or is lost-to-follow up, the vital status data are obtained through public information (death and other registries) per local guidelines and as allowed by local registration.

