2.6.3. Post-Randomization Observation Period

This observation period includes all data from randomization to Day 210/EOS.

Specifically, this observation period will include all events that have occurred after randomization through Day 210/EOS inclusive of all events after completion of double-blind period/Day 180 through Day 210 as well as all events that occurred after subject had withdrew early from the double-blind period through Day 210.

Event: All efficacy events (with respect to deaths, *VTE-related deaths are counted as events for primary efficacy composite endpoint*) that occurred from the date of randomization up to the Day 210/End-of-Study [EOS] (defined in Section 2.5) will be included in the analysis of the Post-Randomization observation period.

- Event time - The time to event is defined as the time from randomization to the time of the first event during this observation period.

Censoring: Subjects who do not experience an event during this observation period will be censored.

Subjects who died during this observation period will be censored as of their death date for endpoint analysis not related to death.

- Censoring time - The time to censoring will be time from randomization to the minimum of (last contact date [up to and including the Day 210 = EOS date defined in Section 2.5], death date [non VTE-related deaths]).

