2.6.4. Post-First Dose Observation Period

This observation period includes all data from the first dose of study drug to Day 210/EOS.

Specifically, this observation period will include all events that have occurred after first dose through Day 210 inclusive of all events after double-blind period completion/Day 180 through Day 210 as well as all events that occurred after subject had withdrew early from the double-blind period through Day 210.

All randomized subjects will be included and the imputation rule for event times for randomized subjects but never dosed described in Section 2.6.2 will also be applied for the analysis of data for this observation period. All events that occur prior to the End-of-Study date will be included in the post-first dose observation period.

Event: All efficacy events (with respect to deaths, *VTE-related deaths are counted as events for primary efficacy composite endpoint*) that occurred from the date of first dose up to the Day 210/End-of-Study[EOS] (Section 2.5) will be included in the analysis of the Post-First Dose observation period.

- Event time - The time to event is defined as the time from first dose date to the time of the first event during this observation period.
 - For randomized subjects but never dosed: The time to event will be defined as the time from randomization to the time of the event during the time in study. This imputation rule will be applied only for the ITT population.

Censoring: Subjects who do not experience an event during this observation period will be censored.

Subjects who died during this observation period will be censored as of their death date for endpoint analysis not related to death.

- Censoring time - The time to censoring is defined as the time from first dose date to the minimum (earliest) of (last contact date [up to and including Day 210 visit date = EOS date defined in Section 2.5], death date [non VTE-related deaths])
 - For randomized subjects but never dosed: The time to censoring will be defined as the time from randomization to the minimum of (last contact date [up to and including Day 210=EOS date, death date [non VTE-related deaths]]).

Examples are illustrated in Figures in the Appendix.

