5.2.5.2. Sensitivity Analysis for Primary Efficacy Composite Endpoint

In this study, all data regarding occurrence of DVT, PE events and vital status (alive/dead) events will be collected for all subjects (completers and early withdrawal) at the Day 210/follow-up visit. Data for the primary efficacy composite endpoint will be missing for subjects for whom the Day 210/follow-up visit is not performed or if the visit was performed but the occurrence of an event was reported as unknown. A conservative approach will be used for subjects who withdrew from the double-blind period and did not have an event during the double-blind period.

In this approach, subjects who withdrew from the double-blind period for any reason other than death and were censored (i.e. had not experienced any VTE-related primary efficacy event during the double-blind period) and have missing or unknown Day210/follow up status will be considered as having a VTE-related event (i.e. not censored). The time from randomization to time of withdrawal will be assumed to be the time to an occurrence of a VTE-related primary efficacy composite event (no specific individual component will be assigned as the worst case).

The sensitivity analysis for the primary efficacy composite endpoint will be based on the '**Up-to-Day 180**' observation period for the ITT analysis population. For the above sensitivity analyses, the cumulative distribution function of the time to first occurrence will be estimated by the Kaplan-Meier method and tested using a log-rank test, stratified by tumor type (APC or non-APC).

The estimate of the hazard ratio (HR), RRR (RRR=100*[1-HR] %) and the 95% confidence intervals for the treatment effect will be provided based on a stratified Cox proportional hazard model (stratification factor: APC or non-APC) and including treatment group as a binary covariate (i.e., rivaroxaban, placebo).

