5.6.2. Analysis Methods

Analysis of the other secondary efficacy endpoints will follow the same approach as in the analysis of the primary efficacy endpoint analysis. These analyses will be based on the ‘Up-to-Day 180’ observation period for the ITT population with censoring as defined above (Section 2.6).

In addition to be above endpoints, the key secondary endpoints (time to symptomatic VTE events or VTE-related deaths, all-cause mortality) will also be analyzed based on the ‘Up-to-Day 180’ observation period for the ITT population.

The cumulative distribution function of the time to first occurrence of each of these endpoints will be estimated by the Kaplan-Meier method and tested using a log-rank test, stratified by tumor type. In addition, a Cox proportional hazard model with treatment and stratification factor as covariates will be fitted. A point estimate along with 2-sided 95% CI for the treatment effect of RRR (RRR=100 x [1-HR] %) will be provided.

The cumulative event rate derived from Kaplan-Meier estimate will also be displayed graphically to evaluate the timing of event occurrence and the consistency of the treatment effect over time. No multiplicity adjustment will be performed for the analysis of these endpoints.

Frequency summary (N, %) of the total number of deaths and the primary cause of death, total number of subjects with myocardial infarction (MI), stroke, and other arterial thrombosis (ATE) events will also be presented for the Up-to-Day 180 observation period.

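### SAP 5.6.2 announces a further analysis of the key secondary endpoints but repeats the Day 180 window, so symptomatic VTE has no analysis of its own to Day 210

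*SAP*

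**What the plan says.** **Windows.** SAP Section 2.6 defines four observation periods. Two reach the end of follow-up. For Post-Randomization, Section 2.6.3 states: "This observation period includes all data from randomization to Day 210/EOS". For Post-First Dose, Section 2.6.4 states: "This observation period includes all data from the first dose of study drug to Day 210/EOS". Section 2.6 gives both a single use: "Post-Randomization and Post-First Dose observation periods: Primary efficacy composite endpoint supportive analyses". Its table lists only Up-to-Day 180 for the key and additional secondary endpoints.

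**Key secondary endpoints.** Section 5.4.2 analyses both in the ITT population over Up-to-Day 180, with a stratified log-rank test, Kaplan-Meier curves and a Cox model. Section 5.6.2 then adds that "the key secondary endpoints (time to symptomatic VTE events or VTE-related deaths, all-cause mortality) will also be analyzed based on" the Up-to-Day 180 period in the ITT population.

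**Ascertainment.** Under Section 1.2, subjects "will be examined by compression ultrasonography (CU) at every 8-week intervals", with a further ultrasound within 2 days of the last dose on permanent discontinuation. Under Section 1.2.1, all subjects "are contacted by telephone for a Day 210/EOS follow-up assessment". Section 5.2.5.2 says that at this visit "all data regarding occurrence of DVT, PE events and vital status (alive/dead) events will be collected for all subjects", both completers and early withdrawals.

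**Mortality at Day 210.** Section 5.7 plans a Cochran-Mantel-Haenszel test of vital status, adjusted for tumor stratum. Section 6.2.3 summarises deaths through Day 210.

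**The concern.** A sentence that introduces an additional analysis should add a window, a population or a method. The one in Section 5.6.2 adds none, so a programmer following it would reproduce the Section 5.4.2 output.

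The consequence is a mismatch. The endpoint carried to Day 210 is the composite that includes asymptomatic proximal DVT, for which no scheduled search is described after Day 180. The two endpoints that a telephone contact can reasonably pick up stop at Day 180.

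The question at stake is whether a reduction in symptomatic VTE on prophylaxis is kept in the month after it ends. VTE after stopping could offset part of the benefit, and no planned analysis gives a hazard ratio for symptomatic VTE through that month. If such an analysis is added only after unblinding, it will be post hoc.

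**Working it through.** **1. The two sentences side by side**

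| | Section 5.4.2 | Section 5.6.2, additional sentence |
|---|---|---|
| Endpoints | symptomatic VTE or VTE-related death; all-cause mortality | the same two |
| Window | Up-to-Day 180 | Up-to-Day 180 |
| Population | ITT | ITT |
| Test | log-rank, stratified by tumor type | the same |
| Model | Cox, treatment and stratification factor as covariates | the same |

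Nothing differs. Composite endpoint #2 in Section 5.6.1 has the same components as the first key secondary endpoint and is also analysed Up-to-Day 180, so it does not fill the gap.

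**2. What the planned 210-day analyses show**

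- *Post-Randomization composite (Sections 2.6.3, 5.2.3).* It counts first events only. A subject with an earlier asymptomatic proximal DVT or incidental PE no longer contributes a later symptomatic event or VTE-related death. Symptomatic first events after Day 180 are counted.
- *Day 210 vital status (Section 5.7).* It compares mortality between arms as alive or dead, without event times or a hazard ratio, and does not address symptomatic VTE.

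That asymptomatic DVT is not systematically sought after Day 180 is an inference from the 8-weekly ultrasound schedule and the telephone contact. The SAP does not say it in one sentence.

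**3. The plan's own power figure**

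Section 1.4 gives 14.5% versus 6.0%, 700 randomized, 20% dropout, two-sided 5% and power above 90%. With 350 × 0.8 = 280 evaluable per arm, a two-proportion calculation gives 91.5%, so the figure reproduces. This point does not depend on it. The rates imply a hazard ratio of ln(0.94)/ln(0.855) = 0.395, the source of the 0.4 used below.

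**4. Scale of the missing month (illustration)**

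From the SAP: about 800 randomized, taken as 400 per arm; symptomatic VTE of at least 12% at 180 days (Section 1.4), applied to placebo. Assumed: constant hazard; hazard ratio 0.4 carried over from the composite to symptomatic VTE; 75% still followed after Day 180; off-drug hazard in the rivaroxaban arm equal to, or twice, the placebo hazard.

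- Placebo cumulative hazard to Day 180: −ln(0.88) = 0.1278. Events: 400 × 0.12 = 48.0.
- Rivaroxaban: 400 × (1 − exp(−0.4 × 0.1278)) = 19.9. Ratio 19.9/48.0 = 0.42.
- Placebo, Days 181–210: 400 × 0.75 × 0.1278 × 30/180 = 6.4.
- Effect simply stops: (19.9 + 6.4)/(48.0 + 6.4) = 26.3/54.4 = 0.48.
- Off-drug hazard doubles: (19.9 + 12.8)/54.4 = 32.7/54.4 = 0.60.

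With an assumed placebo rate of 6%, the three ratios are 0.41, 0.48 and 0.59.

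For mortality the SAP gives no rate. The window is 30/180 = 16.7% longer. With a constant hazard, assumed 180-day risks of 10%, 20% and 30% become 11.6%, 22.9% and 34.0% at Day 210, or about 13, 23 and 32 more deaths in 800 subjects.

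**The case against.** The case for leaving the plan as it is has substance.

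- **The estimand is a 6-month one.** The hypothesis in Section 1.3 concerns treatment for up to 6 months, and the whole testing hierarchy consistently uses ITT and Up-to-Day 180. What is missing is supportive. This stands, and it limits the priority.
- **Mortality to Day 210 is compared.** A reader might infer that deaths after Day 180 go uncompared between arms. They do not: Section 5.7 tests vital status and Section 6.2.3 summarises deaths to Day 210. Over a fixed 30-day extension, a stratified binary comparison covers much of the same ground. Only the time-to-event form is absent.
- **The 210-day composite is informative.** A reader might infer that nothing would reveal a rise in VTE after stopping. The composite includes every symptomatic VTE type and VTE-related death, with a hazard ratio and Kaplan-Meier curves. If no ultrasound is scheduled after Day 180, its late first events would be mainly symptomatic VTE, incidental PE or VTE-related death. It would therefore show most late symptomatic first events. What it loses is symptomatic events in subjects already counted for an asymptomatic DVT or incidental PE, and the SAP gives no basis for estimating how many there are.
- **The scenario figures are not forecasts.** The doubled hazard, 75% retention and 6% rate have no source in the SAP. The Day 180 counts assume complete follow-up while the later counts do not, and the results are ratios of event counts, not hazard ratios.

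One more inference is tempting. The amendment history mentions a post-randomization analysis of the key secondary endpoints, which might suggest that it was later dropped by mistake. The log describes superseded text, so it cannot show what the present sentence was meant to say. The point rests on the current Section 5.6.2 alone.

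**Conclusion.** The point holds in a limited form. The additional analysis announced in Section 5.6.2 is empty. As a result, symptomatic VTE or VTE-related death has no analysis of its own to Day 210, although the data are collected. The 210-day composite covers late symptomatic events in part, and mortality to Day 210 is compared only as a binary outcome.

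The priority is low. No primary conclusion, alpha allocation or power figure changes. On the stated assumptions the symptomatic event-count ratio could move from 0.42 to between 0.48 and 0.60 over the 30 days. This shows only that the month could matter; it does not predict that the benefit is lost. The argument about differing ascertainment also rests on the inference that no ultrasound is scheduled after Day 180, which the protocol's visit schedule should confirm.

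**What to change.** In Section 5.6.2, replace the repeated Up-to-Day 180 window for the key secondary endpoints with the Post-Randomization window, in the ITT population and with the same stratified log-rank test and Cox model. The main use is symptomatic VTE or VTE-related death. For all-cause mortality it complements the Section 5.7 test with event times.

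Update the tables in Sections 2.6 and 5.4.2, and the Section 2.6 sentence that assigns the 210-day windows. Section 2.6.3 already defines event and censoring times to Day 210, but its wording on deaths addresses only the primary composite; a short clause should say that all deaths are events for all-cause mortality. Label the analysis supportive and outside the gated sequence, and keep Up-to-Day 180 as the gated analysis.

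The cost is a few lines of text, the table entries and two more outputs from data already collected, best settled before database lock. The downside is that the added 30 days are off drug and reported by telephone, so the result can only support the Day 180 analysis.

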2.6.1. Up-to-Day-180 Observation Period

This observation period includes data from randomization to Up-to-Day 180 end date (defined in Section 2.5).

Event: All efficacy events (with respect to deaths, *VTE-related deaths are counted as events for primary efficacy endpoint. For the secondary efficacy endpoints, all-cause deaths are counted as events*) that occurred from randomization through the Up-to-Day 180 end date (Section 2.5) will be included in the analysis of this observation period.

- Event time - The time to event is defined as the time from randomization to the time of the first event during this observation period.

Censoring: Subjects who did not experience an event during this observation period will be censored at the last day of their complete assessment for study outcomes.

Subjects who died during this observation period will be censored as of their death date for endpoint analyses not related to death.

- Censoring time - The time to censoring is defined as the time from randomization to the minimum of (last day of their complete assessment for study outcomes during the double-blind period [double-blind completion/withdrawal], death date [non VTE-related deaths for primary efficacy composite endpoint]).

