 - a. If subject experiences an efficacy composite endpoint event (primary or secondary, including VTE-related deaths) after withdrawing from the study and the time to the occurrence of the event is prior to Day 180, then this event and corresponding time to the occurrence of the event will be included in the analysis of primary efficacy composite endpoint. If subject dies (all causes other than VTE-related) after withdrawing from the study and reported on Day 210 but event time is prior to Day 180, then this event and corresponding time to death will be included in the all-cause mortality endpoint analysis
 - b. If a subject does not experience any efficacy composite endpoint event (primary or secondary) in the study, then this subject will be censored. The time to censoring is defined as the time from randomization to the minimum of (last day of their complete assessment for study outcomes during the double-blind period/Day 180 [double-blind withdrawal date for those who withdrew], or death date [censored at death date for analysis not related to the specific death endpoint]).

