5.1.2. Data Handling Rules

The primary efficacy and key secondary endpoint analyses in this study will be based on the ITT analysis population (which includes all randomized subjects). All safety endpoints will be analyzed based on the safety analysis population (which includes all randomized subjects who receive at least one dose of study drug).

Time to event analyses will use censoring rules that apply to subjects with no primary efficacy outcomes during the specified observation periods, or, to subjects who withdrew from the study, or to subjects who die because of reasons other than VTE-related or bleeding, or withdrew informed consent before the end of the predefined treatment duration (Section 2.6 describes in detail all the censoring rules for the different observation periods).

All efforts will be made to collect complete data for all subjects randomized in this study to avoid missing or partial event dates. If the event date is not known, the investigators will provide their best estimate as to when the event occurred based on all the data available for that subject. In the extreme scenario where the event date is partial (missing day and month and year available), the day will be imputed as the first of the month.

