5.4.1. Definition

The key secondary efficacy endpoints defined based on the key secondary efficacy outcomes above are as follows:

- Time to first occurrence of objectively confirmed symptomatic VTE events (symptomatic lower extremity proximal DVT, symptomatic lower extremity distal DVT, symptomatic upper extremity DVT, or symptomatic non-fatal PE) and VTE-related deaths
- Time to all-cause mortality

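### SAP 2.6.1 counts deaths from any cause as events for all secondary efficacy endpoints, which contradicts the definition of the first gated key secondary endpoint and of composites #2 to #4

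*SAP*

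**What the plan says.** Section 2.6.1 sets the event and censoring rules for the Up-to-Day 180 period, on which the primary and all secondary efficacy analyses rest. For the primary composite it counts VTE-related deaths. It then adds, without restriction: "For the secondary efficacy endpoints, all-cause deaths are counted as events". Its censoring-time formula takes the earlier of the last complete outcome assessment and the "death date [non VTE-related deaths for primary efficacy composite endpoint"; no other endpoint is named there.

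The definitions elsewhere are narrower. The table in Section 2.6 gives the first key secondary endpoint as "symptomatic upper extremity DVT, or symptomatic non-fatal PE) or VTE-related deaths", and Section 5.4.1 gives it as "symptomatic upper extremity DVT, or symptomatic non-fatal PE) and VTE-related deaths". The hierarchy in Section 5.5 places this endpoint directly after the primary and before all-cause mortality, each at 0.05.

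Two further general rules deal with deaths:

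- **Section 4.6, scenario 2.** For a non-VTE death after withdrawal but before Day 180, "then this event and corresponding time to death will be included in the all-cause mortality endpoint analysis". Subjects without an event are "censored at death date for analysis not related to the specific death endpoint".
- **Section 5.1.2.** The censoring rules apply, among others, "to subjects who die because of reasons other than VTE-related or bleeding". It adds that "Section 2.6 describes in detail all the censoring rules for the different observation periods".

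Sections 5.4.2 and 5.6.2 also refer to Section 2.6 for censoring.

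**The concern.** Whether a death is censored depends on whether it is an event, and the section to which the analyst is sent says that it is an event for every secondary efficacy endpoint. Followed literally, Section 2.6.1 turns the first gated secondary endpoint into symptomatic VTE or death from any cause. Deaths unrelated to VTE, which prophylaxis would not be expected to change much, would pull its hazard ratio towards 1. This test also decides whether all-cause mortality can be tested formally. Composites #2 to #4 would be altered in the same way, but they carry no multiplicity control.

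**Working it through.** **1. The rule set against each endpoint definition**

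| Secondary efficacy endpoint | Deaths counted under its definition | Fits the 2.6.1 sentence? |
|---|---|---|
| Key secondary 1 (5.4.1; gated) | VTE-related | No |
| Key secondary 2 (5.4.1; gated) | All causes | Yes |
| Composite #1 (5.6.1) | All causes | Yes |
| Composite #2 (5.6.1) | VTE-related | No |
| Composite #3 (5.6.1) | VTE-related, fatal ATE, fatal visceral VTE | No |
| Composite #4 (5.6.1) | VTE-related (major bleeding is also a component) | No |

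The sentence also fails for the single components, ATE and visceral VTE in 5.6.1, none of which counts deaths from all causes. Section 5.5 uses the heading of secondary efficacy endpoints for both gated tests, so the term in 2.6.1 cannot be read as excluding the first one.

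**2. Does 2.6.1 correct itself?** No. The only explicit exclusion of non-VTE deaths is tied to the primary composite. The other censoring sentence covers analyses not related to death, and it is unclear whether a composite that contains VTE-related death is such an analysis.

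**3. Size, as an illustration.** The SAP gives no figure for this endpoint that could be reproduced. The inputs are:

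- Placebo symptomatic VTE at 180 days: 12% (SAP 1.4 calls at least 12% reasonable).
- Rivaroxaban: assumed 5%. This carries over the primary RRR in SAP 1.4: 1 − 6/14.5 = 58.6%, and 12% × (1 − 0.586) = 4.97%.
- Non-VTE mortality m by 180 days: not in the SAP, so it is varied and assumed equal in both arms.
- Constant hazards, so the 180-day cumulative hazard is −ln(1 − p).

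The cumulative VTE hazards are −ln(0.88) = 0.1278 (placebo) and −ln(0.95) = 0.0513 (rivaroxaban).

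Non-VTE deaths censored, as the definition implies: HR = 0.0513/0.1278 = 0.40.

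Non-VTE deaths counted, as 2.6.1 reads: HR = (0.0513 + h)/(0.1278 + h), with h = −ln(1 − m).

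| m | h | HR |
|---|---|---|
| 2.5% | 0.0253 | 0.0766/0.1532 = 0.50 |
| 5% | 0.0513 | 0.1026/0.1791 = 0.57 |
| 10% | 0.1054 | 0.1567/0.2332 = 0.67 |
| 15% | 0.1625 | 0.2138/0.2904 = 0.74 |
| 20% | 0.2231 | 0.2744/0.3510 = 0.78 |
| 25% | 0.2877 | 0.3390/0.4155 = 0.82 |

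Solving for h gives h = (HR × 0.1278 − 0.0513)/(1 − HR). The HR therefore reaches 0.60 at m = 6.2% and 0.70 at m = 12.0%. None of these ratios depends on sample size or dropout.

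**4. Share of events that would be non-VTE deaths.** Use exponential competing times and the SAP's 20% dropout (d = −ln 0.8 = 0.2231). The expected events of one type per subject are its hazard × (1 − e^−T)/T, where T is the sum of the arm's VTE hazard, h and d. At m = 8.5% (h = 0.0888) the factor (1 − e^−T)/T is 0.809 on placebo and 0.838 on rivaroxaban. VTE events per pair of subjects, one in each arm: 0.1278 × 0.809 + 0.0513 × 0.838 = 0.146. Non-VTE deaths: 0.0888 × (0.809 + 0.838) = 0.146. Half of the counted events would then be deaths unrelated to VTE.

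**The case against.** The best counter-argument is that nobody would program the literal sentence. The objectives, the 2.6 table, Sections 5.4 and 5.4.1, the 5.4.2 table and the hierarchy all limit the first key secondary endpoint to VTE-related death. Composite #1 is expressly labelled where all-cause mortality is wanted. Section 2.6 describes time windows and refers to Section 5 for detail, and 5.4.2 cites it for censoring, not for event definitions. Read literally, the sentence would make any death an event even for upper extremity DVT alone, which would leave the censoring rule for analyses unrelated to death with no secondary endpoint to apply to. Rule 2b of Section 4.6 already censors by endpoint-specific death type. Section 5.1.2 is itself loose: taken literally, it would censor non-VTE deaths for all-cause mortality as well.

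Most of this stands as evidence of intent, and it is why the point is one of wording and not of design. It does not remove the conflict. The SAP gives no order of precedence, and Section 5.1.2 names Section 2.6 as the place where all the censoring rules are described. There the exclusion of non-VTE deaths stops at the primary composite. The analyst of a gated test should not have to choose between sections. It is also fair that the hazard ratios describe an analysis that was probably not intended and rest on a mortality range the SAP does not supply. They show what following the sentence would do, not what is expected to happen.

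**Conclusion.** The sentence in Section 2.6.1 is wrong as written. It agrees with all-cause mortality and composite #1 and contradicts the first gated key secondary endpoint and composites #2 to #4. The Section 5 definitions and Section 4.6 make the intended reading likely, so the correction is editorial, but it should be made because an alpha-controlled test is affected.

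Under the illustrative assumptions (12% against 5% symptomatic VTE, equal non-VTE mortality in both arms, constant hazards), following the sentence would move the hazard ratio from 0.40 to between 0.57 and 0.82 over 5% to 25% non-VTE mortality. The mortality range and the rivaroxaban rate are assumptions. No claim about power is made, and the primary analysis and its sample size are unaffected.

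**What to change.** In Section 2.6.1:

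1. Replace the sentence on secondary endpoints with a rule that, for each one, only the deaths belonging to its definition in Section 5.4.1 or 5.6.1 are events, and that deaths from any cause count only for all-cause mortality and composite #1.
2. Extend the bracket in the censoring-time formula from the primary composite to every endpoint: a subject whose death is not a component is censored at the earlier of the last complete outcome assessment in the double-blind period and the death date.
3. Make the preceding sentence on censoring at death refer to that same minimum. A subject who withdrew and died later then gains no event-free time after assessment ended. This matches the formula already in 2.6.1 and rule 2b of Section 4.6.

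The cost is SAP wording only, with no new data and no additional analyses.
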